Study Title: Umbilical Trocar Site Is the Usual Suspect for Trocar Hernia After LaparoscopicCholecystectomy: A Prospective StudyNCT ID: Not yet assigned.

Date: April 15, 2025

CLINICAL STUDY REPORT (CSR)

Study Title: Umbilical Trocar Site Is the Usual Suspect for Trocar Hernia After Laparoscopic
Cholecystectomy: A Prospective Study
Study Type: Prospective, randomized controlled trial
Study Duration: April 15, 2022 – June 15, 2024
Study Location: Umraniye Training and Research Hospital, Department of General Surgery
Principal Investigator: Ass. [name]. [name]
ClinicalTrials.gov ID: Not yet assigned

1. Study Synopsis

Objective:

To evaluate whether the site of gallbladder retrieval (umbilical vs. epigastric) affects the incidence of trocar site hernia (TSH) following laparoscopic cholecystectomy (LC), and to identify risk factors for TSH.

Design:

Prospective, randomized, single-blind, controlled study with two parallel arms.

Participants:

110 patients undergoing elective LC for gallstone disease were randomized. After accounting for conversions and loss to follow-up, 100 patients (50 in each group) were included in the final analysis.

Intervention:

Standard 4-port LC performed. Gallbladder retrieved via either:

Group U: Umbilical trocar (10 mm)

Group E: Epigastric trocar (10 mm)

Primary Outcome:

Incidence of trocar site hernia at 12-month follow-up.

Secondary Outcomes:

Gallbladder retrieval time

Postoperative pain scores (VAS at 6 and 24 hours)

Risk factor analysis for TSH development

Key Results:

TSH occurred in 12% (6/50) of umbilical group and 10% (5/50) of epigastric group (P = 1.00).

All hernias were located at the umbilical site.

Epigastric retrieval was faster (P = 0.013) but associated with more early pain (P = 0.027).

Fascial widening was the only independent risk factor for TSH (OR = 4.08, P = 0.05).

2. Study Design

Randomization:

Performed via the Alea Randomisation mobile app. Allocation was sealed and revealed intraoperatively before specimen retrieval.

Blinding:

Patients were blinded. Surgeons were not blinded due to the nature of the procedure, but were unaware of group allocation until extraction.

Surgeon Consistency:

All surgeries were performed by three experienced general surgeons using standardized techniques.

Antibiotic Prophylaxis:

Intravenous cefazolin 2 g administered preoperatively.

3. Inclusion / Exclusion Criteria

Inclusion:

Age ≥ 18

Gallstone disease

No significant systemic comorbidities

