
Exclusion:

Age < 18

Conversion to open surgery

Acute cholecystitis

Prior common bile duct surgery

Presence of diastasis recti or umbilical hernia

4. Surgical Technique

Standard LC using:

10 mm umbilical camera port

10 mm epigastric port

Two 5 mm subcostal ports

Fascial closure was performed only at the umbilical site using polyglactin sutures.

Epigastric port sites were not sutured.

Gallbladder retrieval performed using a bag.

5. Postoperative Management & Follow-Up

Pain Control:

IV paracetamol and tramadol postoperatively. VAS recorded at 6 and 24 hours.

Discharge & Follow-up:

Routine discharge on Day 1 if no complications. All patients followed for 12 months.

Hernia Diagnosis:

Symptomatic patients evaluated with ultrasonography. Asymptomatic patients underwent

scheduled USG at 6 and 12 months.

6. Statistical Analysis

- Data analyzed with SPSS v26 and RStudio.
- Categorical data were analyzed using Fisher's exact or Chi-square tests
- Continuous variables were compared using Student's t-test or Mann–Whitney U test
- Univariate and multivariate logistic regression performed to evaluate TSH risk factors.
- Significance threshold: P < 0.05

7. Results Summary

Demographics:

Age, BMI, and other baseline factors were comparable between groups.

Outcomes:

- Hernia rate: 6 in Group U, 5 in Group E (all at umbilicus)
- Retrieval time shorter in Group E (P = 0.013)
- Pain lower in Group U at 6h (P = 0.027)
- No difference in 24h VAS scores
- Multivariate Analysis:
- Fascial widening was the only independent predictor of TSH (OR = 4.08, P = 0.05)

8. Discussion

- All trocar site hernias (TSH) occurred at the umbilical site, regardless of extraction route.
- This confirms the umbilicus as the most vulnerable location for hernia development after
- laparoscopic cholecystectomy.
- Epigastric extraction avoided direct stress on the umbilical site and was associated with no
- hernias at the epigastric port.
- Gallbladder retrieval was faster via the epigastric route, offering operative efficiency.
- Early postoperative pain (6h) was slightly higher with epigastric extraction but not clinically
- limiting.
- Fascial widening during extraction was the only independent risk factor for TSH.
- These findings support preferential use of the epigastric port for specimen retrieval to
- minimize hernia risk.

9. Conclusion

While trocar site selection did not statistically alter the incidence of hernia, all hernias occurred at

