the umbilicus, highlighting its vulnerability. Fascial widening during extraction was a key

modifiable risk factor. Epigastric retrieval may offer operative efficiency, but at a slight cost in

postoperative discomfort.

10. Ethical Considerations

- Approved by the Clinical Research Ethics Committee of Istanbul University of Health
- Sciences, Umraniye Training and Research Hospital.
- All participants provided written informed consent.
- Study conducted in accordance with the Declaration of Helsinki.
- No funding received. No conflicts of interest declared.

STATISTICAL ANALYSIS PLAN (SAP)

Study Title: Umbilical Trocar Site Is the Usual Suspect for Trocar Site Hernia After

Laparoscopic Cholecystectomy: A Prospective Study

Version: 1.0

Prepared by: [name]

Study Sponsor: Umraniye Research and Training Hospital

Principal Investigator: Ass. [name]. [name]

1. Study Overview

This is a prospective, randomized, controlled clinical trial evaluating the incidence of trocar site hernia (TSH) in patients undergoing laparoscopic cholecystectomy, comparing gallbladder extraction via the umbilical versus epigastric port.

2. Study Objectives

Primary Objective:

To assess whether the site of gallbladder retrieval (umbilical vs. epigastric trocar) affects the incidence of trocar site hernia.

Secondary Objectives:

To compare postoperative pain levels at 6 and 24 hours between groups

To assess gallbladder retrieval time

To identify independent risk factors for the development of trocar site hernia

3. Endpoints

Primary Endpoint:

Incidence of trocar site hernia (clinical or ultrasonographic diagnosis within 12 months)

Secondary Endpoints:

- Gallbladder retrieval time (in seconds)
- Visual Analogue Scale (VAS) pain scores at 6 and 24 hours postoperatively
- Occurrence of fascial widening and its association with TSH

• Logistic regression model identifying independent risk factors for TSH

4. Analysis Populations

Intention-to-Treat (ITT):

All randomized patients, excluding those who converted to open surgery or were lost to follow-

up.

Per Protocol (PP):

Patients who completed surgery and 12-month follow-up without major protocol deviations.

5. General Statistical Methods

- Statistical significance threshold set at P < 0.05 (two-sided).
- All statistical analyses will be performed using SPSS v26.0 and RStudio v4.2.0.
- Results will be reported with appropriate confidence intervals (CIs) and effect sizes when
- applicable.

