6. Data Handling and Assumptions

Missing Data:

No imputation will be performed.

Patients lost to follow-up will be excluded from analysis of outcomes they did not complete.

Outliers:

Checked visually (boxplots, scatterplots).

No exclusions unless clinically justified.

Normality Testing:

Shapiro-Wilk test used for continuous variables.

7. Baseline and Demographic Comparisons

Descriptive statistics: mean ± SD for normally distributed data; median (min-max) for non-

normal data; frequency (%) for categorical variables.

Comparisons:

• Categorical variables: Chi-square or Fisher's exact test

• Continuous variables: Student's t-test or Mann–Whitney U test depending on distribution

8. Primary Endpoint Analysis

Incidence of TSH:

Compared between the umbilical and epigastric groups using Fisher's exact test.

9. Secondary Endpoint Analyses

- Gallbladder retrieval time: Compared using Mann–Whitney U test (non-normal distribution
- anticipated).
- Postoperative pain scores (VAS at 6h and 24h): Assessed separately at both time points.
- Compared using Mann–Whitney U test.
- Exploratory regression analyses: Univariate logistic regression to identify factors associated
- with TSH Variables with P < 0.2 or known clinical relevance will be entered into a
- multivariate logistic regression model.
- Odds Ratios (OR), 95% CI, and P-values will be reported.

10. Subgroup Analyses

Subgroup analysis will be performed for patients in the umbilical extraction group to evaluate the

impact of fascial widening on TSH incidence using logistic regression.

11. Software

All analyses will be conducted using:

- SPSS v26.0 (IBM Corp., Armonk, NY, USA)
- RStudio v4.2.0 (The R Foundation)

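### The claim that the umbilicus is the most vulnerable port rests on a count with no test or interval; a post hoc port-level analysis could support only a narrower claim, about the ports as handled

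*Combined protocol and SAP*

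**What the plan says.** The primary objective in SAP Section 2 is whether the retrieval site affects the incidence of trocar site hernia. The primary endpoint in SAP Section 3 counts any such hernia within 12 months and names no port. SAP Section 8 then gives a single test: "Compared between the umbilical and epigastric groups using Fisher's exact test". SAP Section 9 adds patient-level logistic regressions for risk factors. SAP Section 10 adds an analysis of fascial widening within the umbilical arm. None of these compares one port with another.

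CSR Section 4 gives every patient a 10 mm umbilical camera port and a 10 mm epigastric port, handled differently: "Fascial closure was performed only at the umbilical site using polyglactin sutures", and "Epigastric port sites were not sutured". CSR Section 5 schedules ultrasonography at 6 and 12 months for asymptomatic patients but does not say which ports are examined.

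The CSR synopsis reports that "TSH occurred in 12% (6/50) of umbilical group and 10% (5/50) of epigastric group (P = 1.00"), and that every hernia was umbilical. CSR Section 8 concludes: "This confirms the umbilicus as the most vulnerable location for hernia development after" this operation. It also cites the absence of epigastric hernias and favours the epigastric port for retrieval as a way to minimise hernia risk. CSR Section 9 says that the choice of site did not statistically alter incidence.

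**The concern.** There are two questions here. One is whether retrieval route changes the hernia rate, which is a comparison between randomised arms. The other is which port herniates, which is a comparison between two ports in the same patient. The plan addresses the first. The Discussion's site statement concerns the second, for which nothing is planned and no test or interval is reported. The between-arm P value cannot fill the gap: it depends only on how many patients in each arm had a hernia, so it would be the same whichever ports had failed.

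The two site statements also differ in strength. The excess at the umbilicus is large relative to the number of events. The reassurance about the epigastric port rests on a zero count, and the count that matters for retrieval through that port comes from 50 patients. The report gives the counts and denominators, so a reader could derive the limits, but it presents both statements in the same confident terms.

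The word 'confirms' then attributes the pattern to location, when suturing and camera use went with location in every patient.

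**Working it through.** **Inputs.** "110 patients undergoing elective LC for gallstone disease were randomized"; "100 patients (50 in each group) were included in the final analysis" (CSR Section 1). Hernias: 6 in Group U and 5 in Group E, all umbilical (CSR Section 7). Both 10 mm ports in every patient (CSR Section 4). Two-sided 0.05 threshold (SAP Section 5).

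**Assumptions not in the documents.** (a) Each affected patient had one hernia. (b) Both 10 mm ports were scanned in all 100 patients.

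**1. The reported figure.** Fisher's exact test on 6/50 v 5/50: with 11 events in two equal arms, the 6:5 and 5:6 splits are jointly the most probable tables. No table is more probable than the observed one, so the two-sided P is 1.00. The stated value reproduces. The arm difference is 12% − 10% = 2 points (Newcombe 95% CI −11.0 to 15.1).

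**2. Within-patient comparison of ports.** Let b be the number of patients with an umbilical hernia only and c the number with an epigastric hernia only. When c = 0, the exact McNemar P is 2 × 0.5^b.

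| Patients | b v c | Calculation | P |
|---|---|---|---|
| All 100 | 11 v 0 | 2 × 0.5^11 | 0.00098 |
| Group U | 6 v 0 | 2 × 0.5^6 | 0.031 |
| Group E | 5 v 0 | 2 × 0.5^5 | 0.0625 |

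The pooled paired risk difference is 11.0 points (Tango 95% CI 6.3 to 18.6).

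**3. Exact limits per port.** For zero events in n patients, the upper two-sided 95% limit is 1 − 0.025^(1/n).

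- Epigastric port used for retrieval, 0/50: 1 − 0.025^(1/50) = 7.1%.
- Epigastric port, all patients, 0/100: 1 − 0.025^(1/100) = 3.6%.
- Umbilical port, all patients, 11/100: Clopper-Pearson 5.6% to 18.8%.

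**4. Sensitivity to assumption (b).** Suppose k epigastric-only hernias were missed. The comparison becomes 11 v k, with P = 2 × Pr(X ≥ 11), X binomial (11 + k, 0.5).

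- k = 1: 2 × (12 + 1)/4096 = 0.0063
- k = 2: 2 × (78 + 13 + 1)/8192 = 0.022
- k = 3: 2 × (364 + 91 + 14 + 1)/16384 = 0.057

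The pooled result stays below 0.05 with two missed hernias and loses that with three.

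**The case against.** The strongest reply is that SAP Section 8 contains no error. The objective is about retrieval route, and a between-arm Fisher test on hernia at any port answers it. Port vulnerability was neither an objective nor an endpoint. That stands: a reader might infer that the primary analysis is wrong, and the documents do not support this. The fault lies in the CSR wording. The phrase about the most vulnerable location is also the Discussion's; the title makes only the looser claim of a usual suspect.

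A second reply is that the counts are already known. Adding a paired test to the primary endpoint section now would make a data-driven analysis look planned. That stands too, and decides where the test belongs.

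A third is that the pooled P of 0.001 overstates the case. In Group U the umbilicus was also the retrieval port, so retrieval adds to its risk. In Group E, where the epigastric port carried the retrieval, 5 v 0 gives P = 0.0625, above the plan's threshold. Whether the epigastric port was scanned in everyone is not stated. These points stand as limits to report with the result. They do not remove the gap, since the CSR makes the site claim with no test at all.

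The last is that the documents set no threshold by which an upper limit of 7.1% would be too high. That is so. The interval should be given without a label of clinical relevance.

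**Conclusion.** The point holds as one about the CSR's site claim. No planned analysis compares ports, and the statements that the umbilicus is confirmed as most vulnerable and that no hernia arose at the epigastric port come without a test or an interval.

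Under the two stated assumptions, the data show an umbilical excess under this technique (11 v 0, P = 0.001). They bound epigastric hernia only loosely: up to 7.1% after retrieval through that port, and up to 3.6% over all patients. The ten randomised patients not analysed (110 − 100) have no reported site status.

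Two stronger inferences are not supported:

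- *That the umbilicus is intrinsically weaker.* Suturing and camera use coincide with location in every patient, so no analysis of these data can separate them.
- *That a small port-level P value favours one retrieval route.* Only the arm comparison bears on that, and it shows 12% v 10%, P = 1.00. The Discussion's statement about minimising hernia risk and the Conclusion's statement that incidence was not statistically altered must be reconciled.

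**What to change.** Leave SAP Section 8 as it is. In the CSR:

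1. Add a port-level analysis clearly labelled post hoc: hernia yes or no at each 10 mm port, compared within patient by exact McNemar, pooled and by arm, with exact confidence intervals per port. Include 0/50 (0 to 7.1%) and 0/100 (0 to 3.6%) for the epigastric port.
2. State which ports were scanned and in how many patients, and whether any patient had more than one hernia. Give the sensitivity to missed epigastric-only hernias (two missed P = 0.022, three missed P = 0.057).
3. In CSR Section 8, replace 'confirms' with wording limited to the ports as handled in this trial, naming suturing and camera use as inseparable from location.
4. State that the port-level result does not bear on whether retrieval route changes incidence, and reconcile CSR Sections 8 and 9 on that point.

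The cost is one short analysis and a few sentences, with no new patients, provided that port-level scan results were recorded. If they were not, the report should say so and present the paired result as conditional. The downside is that the location claim becomes narrower.

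### SAP section 9 lets intra-operative results share a model with pre-operative factors; with fascial widening in that model, the claim that it is the only independent risk factor is unsupported

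*Combined protocol and SAP*

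**What the plan says.** SAP section 2 makes finding independent risk factors for hernia a secondary objective. SAP section 3 lists two related secondary endpoints: "Occurrence of fascial widening and its association with TSH" and "Logistic regression model identifying independent risk factors for TSH". Widening is therefore itself an outcome of the trial.

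SAP section 9 describes the modelling as "Exploratory regression analyses: Univariate logistic regression to identify factors associated" with hernia, followed by an entry rule: "with TSH Variables with P < 0.2 or known clinical relevance will be entered into a" multivariable logistic model. No candidate variable is named, and candidates are not restricted to those known before surgery. ORs, 95% CIs and P-values are to be reported. SAP section 10 adds a separate logistic regression of hernia on widening, in the umbilical extraction group only.

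CSR section 7 gives, under its multivariable heading, "Fascial widening was the only independent predictor of TSH (OR = 4.08, P = 0.05". CSR section 8 repeats it as "Fascial widening during extraction was the only independent risk factor for TSH", and CSR section 9 describes widening as modifiable. CSR section 2 says that allocation was disclosed during the operation, before the specimen was retrieved.

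**The concern.** Widening comes after the allocation is revealed and after every patient characteristic is fixed. It can be a consequence of the retrieval route, or of any feature that makes the gallbladder harder to extract. If such a feature raises hernia risk by causing widening, a model containing both credits that path to widening. The feature's own coefficient is then only what remains, its direct effect, which may be nil.

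That is harmless if the only question is whether widening goes with hernia. It matters once the result is stated with *only*, because that word is a claim about every other candidate. A factor known before the operation, and useful for saying who is at risk, could look unimportant because its own consequence is in the model. Neither the SAP nor the CSR carries this caveat.

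**Working it through.** **Inputs from the documents.** 100 patients analysed, 50 per arm; hernias 6/50 and 5/50, so 11 in all (CSR section 1); widening OR 4.08, P = 0.05 (CSR section 7). The documents give no number of patients with widening, no covariate list, no univariate results and no CI.

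**1. Arm comparison.** OR = (6 × 45)/(44 × 5) = 270/220 = 1.23. SE of the log OR = √(1/6 + 1/44 + 1/5 + 1/45) = 0.642, giving a Wald 95% CI of 0.35 to 4.32. Fisher's exact P = 1.00, as the CSR states.

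**2. Widening OR.** It cannot be refitted. By back-calculation, SE = ln(4.08)/1.96 = 1.406/1.96 = 0.717, so the 95% CI is about exp(1.406 ± 1.96 × 0.717) = 1.00 to 16.6. Simple 2×2 tables with 11 hernias in 100 come close. With 4 hernias among 15 widened, OR = (4 × 78)/(7 × 11) = 4.05. With 8 among 43, OR = (8 × 54)/(3 × 35) = 4.11. The figure is plausible but not verifiable.

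**3. Order of events.** Patient features are fixed first, then allocation is disclosed, then extraction with or without widening, then hernia within 12 months. The entry rule in SAP section 9 lets variables from any of the first three stages into one model. CSR section 7 shows that a variable from the third stage was in it.

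**4. Illustration, factor acting only through widening.** Assumptions: a baseline factor present in 30% raises widening from 15% to 60%; overall hernia risk 11%; widening OR 4.08; no direct effect.
- Overall widening = 0.30 × 0.60 + 0.70 × 0.15 = 28.5%.
- Solving 0.715 × r0 + 0.285 × r1 = 0.11, with the odds of r1 equal to 4.08 times the odds of r0, gives r0 = 6.5% and r1 = 22.2%.
- Hernia risk with the factor = 0.60 × 22.2% + 0.40 × 6.5% = 15.9%.
- Hernia risk without it = 0.15 × 22.2% + 0.85 × 6.5% = 8.9%.
- Total OR = (0.159/0.841)/(0.089/0.911) = 1.94. Given widening, the OR is 1.0 by assumption.

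The total OR is 1.57 if widening is 20% v 50%, and 2.67 if it is 10% v 80%. In simulated trials of 100 patients the median OR was about 1.9 without widening in the model and about 1.0 with it.

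**5. Other assumptions.** Factor in 50%, widening in 20% to 50%, OR of factor on widening 2 to 8:

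| Direct OR of factor | Total OR | OR given widening |
|---|---|---|
| 1 | 1.21 to 1.85 | 1.0 |
| 2 | 2.35 to 3.62 | about 2.0 |

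**6. Chance that the factor reaches P < 0.05 with 100 patients** (factor in 50%, widening in 30%):

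| Direct OR | OR of factor on widening | Without widening in model | With widening |
|---|---|---|---|
| 1 | 4 | 6% | 4% |
| 1 | 8 | 10% | 2% |
| 2 | 4 | 25% | 8% |
| 2 | 8 | 35% | 6% |

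In the step 4 scenario the chance without widening in the model is about 18% (about 10% to 34% across its range).

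**7. Information available.** Events per covariate are 11/2 = 5.5, 11/3 = 3.7 and 11/5 = 2.2 for two, three and five covariates.

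**The case against.** The strongest reply has five parts.

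- SAP section 9 names no variable, and no document shows that arm or any cause of widening was in the model. This stands. Only the presence of widening is documented, so attenuation is a possibility.
- The plan already has total effects. The univariate models leave widening out and are to be reported with CIs, and the Fisher test gives the randomised effect of arm. This largely stands. However, the CSR does not show the univariate results, they do not adjust pre-operative factors for one another, and the headline conclusion comes from the multivariable model.
- Power is the larger problem. This stands. Even without widening in the model, the illustrated factor is missed in most trials. In the step 4 scenario it passes the P < 0.2 screen only about 41% of the time (29% to 59%), so it might never be entered beside widening except by the clinical-relevance route.
- The adjusted OR of 1.0 in step 4 restates the assumption. This is true. The step shows the size of the gap on assumed rates and is not evidence that the gap occurred.
- *Independent* conventionally means associated after adjustment, and an intra-operative variable is legitimate for prediction or a direct effect. SAP section 9 also calls the regression exploratory. This is fair, but the SAP does not say which aim applies. Sections 2 and 3 make the regression a secondary objective and endpoint, and the CSR carries it into its key results and conclusion, where calling widening modifiable is a causal reading.

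SAP section 10 does not settle the matter: it studies widening in one arm and gives no total effect for any other factor.

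**Conclusion.** The point holds as a minor one. The SAP's entry rule mixes pre-operative factors with intra-operative results, and the reported model contained widening. The total effect of any upstream factor entered beside it may be understated, so the model cannot support *only*. On the assumed inputs the understatement runs from slight (total OR 1.21 shown as 1.0) to marked (2.67 shown as 1.0, or 3.62 shown as about 2.0). The actual size is unknown without the covariate list and univariate results.

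A reader might infer more, in three ways that the documents do not support:

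- That other risk factors were in fact adjusted away. Nothing shows this, and with 11 hernias low power alone could leave them non-significant.
- That an effect of retrieval route was hidden. The comparison was null before any adjustment: "TSH occurred in 12% (6/50) of umbilical group and 10% (5/50) of epigastric group (P = 1.00".
- That the association of widening with hernia is an artefact of this modelling. The point concerns the other coefficients. The widening estimate is imprecise for separate reasons.

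The primary Fisher comparison is unaffected.

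**What to change.** - In SAP section 9, name the candidate variables and mark each as pre-operative or intra-operative.
- Fit one small logistic model with randomised arm and a few pre-operative factors, without widening. Use it for statements on who is at risk, and report it beside the univariate ORs with 95% CIs.
- In the model that contains widening, interpret only the widening coefficient, as an association.
- Remove *only* from CSR sections 1, 7 and 8. State that factors null in that model are not shown to be unrelated to hernia, both because widening is in the model and because there are only 11 events.

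The cost is one extra model on existing data and a few sentences. The downside is that, with 11 hernias, the pre-operative model must be very small and its intervals will be wide, so it may also be inconclusive.

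### The CSR presents fascial widening as the only independent, modifiable risk factor, but the support is an exploratory regression on at most 11 hernias with P = 0.05 and no confidence interval

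*Combined protocol and SAP*

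**What the plan says.** SAP 2 lists as a secondary objective "To identify independent risk factors for the development of trocar site hernia", and SAP 3 makes the logistic model a secondary endpoint, alongside widening and its association with hernia. SAP 9 nevertheless describes the regression as exploratory. Its entry rule reads "with TSH Variables with P < 0.2 or known clinical relevance will be entered into a" multivariate model. It lists no candidates, sets no limit on model terms and names no small-sample method. It promises the OR, 95% CI and P-value. SAP 5 sets two-sided significance at P below 0.05. SAP 10 plans a separate logistic regression of hernia on widening within the umbilical group.

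The CSR (section 1, Key Results) states "Fascial widening was the only independent risk factor for TSH (OR = 4.08, P = 0.05". CSR 7 repeats the figures under multivariate analysis. CSR 8 says "Fascial widening during extraction was the only independent risk factor for TSH", and CSR 9 says "Fascial widening during extraction was a key" modifiable risk factor. CSR 7 gives the events as "Hernia rate: 6 in Group U, 5 in Group E (all at umbilicus". On timing, CSR 2 says "Allocation was sealed and revealed intraoperatively before specimen retrieval".

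**The concern.** Four words in the CSR go beyond what the analysis can show. Only implies that the other candidates were shown not to matter. Independent implies adequate adjustment. Key and modifiable imply a cause that the surgeon can act on. With so few events, the model can show none of these. The qualifier exploratory, which SAP 9 carries, is missing from the CSR.

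The reader also lacks the information needed to discount the claim: the CI, the exact P, the candidate list, the terms entered, the number of patients in the model, the number with widening, and the port at which widening was recorded. The port matters because "All hernias were located at the umbilical site". Widening at an epigastric port and widening at the umbilicus are different exposures for an umbilical hernia.

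The stakes are the CSR's secondary conclusion. The randomised comparison showed no difference (P = 1.00), so widening is the report's one positive claim about which patients herniate. The Discussion bullet that follows it draws a recommendation on the extraction port from these findings.

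**Working it through.** **Inputs from the documents.** Hernias 6/50 in Group U and 5/50 in Group E, 11 of 100 in total (CSR 1 and 7); multivariate OR 4.08, P = 0.05 (CSR 1 and 7); threshold P < 0.05, two-sided (SAP 5). **Not given:** number widened, its split by arm, candidates, model terms, patients in the model, type of test behind P.

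**1. What can be reproduced.** Fisher's exact test on 6/50 against 5/50 gives P = 1.00, as printed. The adjusted OR cannot be refitted from the figures given.

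**2. Implied interval, assuming a Wald P.** SE = ln(OR)/z.
- ln(4.08) = 1.406; z for P = 0.05 is 1.960; SE = 1.406/1.960 = 0.717.
- 95% CI = exp(1.406 ± 1.960 × 0.717) = 1.00 to 16.6.
- If P was rounded from 0.045: z = 2.005, SE = 0.701, CI 1.03 to 16.1.
- If P was rounded from 0.0549: z = 1.920, SE = 0.732, CI 0.97 to 17.1.

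The printed figure therefore fits a result on either side of the threshold.

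**3. Dependence on the test.** These single-predictor tables have 11 events in 100 and an OR near 4. They are illustrations, because the number widened is unknown.

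| Hernias, widened v not | OR | Wald P | Likelihood-ratio P | Fisher P |
|---|---|---|---|---|
| 5/21 v 6/79 | 3.80 | 0.045 | 0.052 | 0.050 |
| 8/43 v 3/57 | 4.11 | 0.047 | 0.034 | 0.052 |
| 9/55 v 2/45 | 4.21 | 0.076 | 0.048 | 0.105 |

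The profile-likelihood interval is 0.99 to 14.2 for the first table and 1.01 to 28.6 for the third. The choice of test alone can move P across 0.05, and the upper limit can lie well above 16.6.

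**4. Information per model term.** With 11 events there are 11/2 = 5.5, 11/3 = 3.7, 11/4 = 2.8 and 11/5 = 2.2 events per term for 2, 3, 4 and 5 terms. If widening occurred only in Group U, a group-adjusted estimate for it would rest on the 6 Group U events.

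**5. Selection from an unlisted set.** The SAP 9 rule was simulated with no true predictor: 100 patients, 11 events, independent candidates, entry at P < 0.2, then multivariable P < 0.05. At least one factor reached significance in 13%, 25% and 34% of trials with 4, 8 and 12 candidates. The candidate counts are assumed. The number of candidates drives the rate, not the entry screen.

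**6. The unreported Group U analysis.** Among all 2×2 tables with 6 hernias in 50 and no empty cell, 10 have an OR between 3.5 and 4.7. Example, 4/18 against 2/32:
- OR = (4 × 30)/(14 × 2) = 4.29, and ln OR = 1.455.
- SE = √(1/4 + 1/14 + 1/2 + 1/30) = 0.925.
- z = 1.455/0.925 = 1.57, so P = 0.12.

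Over the 10 tables, Wald P runs from 0.10 (3/11 v 3/39) to 0.27 (1/3 v 5/47), likelihood-ratio P from 0.10 to 0.31, and Fisher P from 0.11 to 0.38.

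With a true OR of 4 and 6 hernias, the chance of an empty cell is 2%, 3.5%, 10% and 21% when 10, 15, 20 and 25 of the 50 were widened. Ordinary logistic regression then has no finite OR.

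**The case against.** The strongest defence is that the plan itself is fairly sound here. SAP 9 calls the regression exploratory and promises the OR, CI and P; followed as written, it would have prevented most of the harm. The main fault lies in how the CSR reports and labels the result. That stands, and it is why the fix falls mainly on the CSR. It is also fair that this is a secondary result and that CSR 9 admits that site did not statistically alter incidence.

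The same defence rules out several stronger readings:

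- *Widening is a chance finding.* The selection figures show how easily an unlisted candidate set yields a significant factor. They do not show that this one is false, and SAP 3 and SAP 10 name widening specifically.
- *Widening was pre-specified, so selection is no issue.* The SAP is marked version 1.0 with no date, and the file is dated April 15, 2025, after the study ended on June 15, 2024. The documents show neither that widening was specified before the results were known nor that it was added afterwards.
- *The label rests on the 6-event subgroup.* The CSR credits OR 4.08 to the multivariate analysis. The Group U tables are unadjusted and do not show where that OR came from. They show only how little the missing analysis could establish if its OR were similar; weaker significance in half the sample is to be expected.
- *The 95% CI is 1.0 to 16.6.* That is a back-calculation under a Wald assumption, not a reported interval.
- *The planned model should be replaced.* A two-term model chosen now would follow the results and drop all other adjustment. It belongs beside the SAP 9 model, not in its place.

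**Conclusion.** The point holds as one of precision, reporting and labelling. At most 11 hernias, a P printed at the threshold and an unreported CI cannot establish widening as the only independent or a key modifiable risk factor, and they cannot rule out other factors. On the Wald reading, the figures are compatible with almost no association and with one of about 16-fold. The event count of 11 is a maximum, because the CSR does not say that all 100 patients entered the model.

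Widening arose during extraction and was not randomised, so its association with hernia is observational; modifiable is a causal word that this analysis does not earn. A reader might infer that the trial's main result is undermined. It is not: the SAP 8 comparison of 6/50 with 5/50 does not depend on this model.

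The missing CI, the missing SAP 10 result, the borderline P, the event count and the lost exploratory label can all be read directly from the documents. The interval limits rest on the assumed test, and the selection and empty-cell rates on an assumed candidate count and number widened.

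**What to change.** In the CSR:
- Report the SAP 9 model in full: every candidate examined, the terms entered, patients and events used, OR, 95% CI, and P to three decimals.
- Report the SAP 10 Group U result, by Firth or exact methods if a cell is empty or sparse.
- Give widening, and hernias by widening, for each arm, and state the port at which widening was recorded.
- Describe widening as an exploratory association, remove the words only, independent, key and modifiable, and state that at most 11 events can neither establish independent risk factors nor rule out others.

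As a sensitivity analysis, labelled post hoc, add a Firth logistic regression of hernia on widening and randomised group with profile-likelihood CIs. Widening follows allocation, so state that the group coefficient in this model is not the total effect of extraction site. If widening was recorded at different ports in the two arms, do not pool it into one OR. SAP 8 stays the primary analysis.

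The cost is a small re-run on existing data in R, which SAP 5 already names, together with CSR wording and a dated note declaring the added analysis. The secondary conclusion becomes less favourable. Firth shrinks the OR somewhat (4/18 against 2/32 gives 4.29 by maximum likelihood and 3.79 by Firth), and the added model may be very imprecise. In simulations with a true OR of 4.08, the median CI was 1.15 to 16.3 with 30% widened in both arms, and 0.57 to 31.0 with widening in half of Group U only. These prevalences are assumed.
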